5.3 HANDLING OF MISSING DATA

The primary and all secondary end points will be analysed on a mITT basis.

During the study, participants may be lost to follow-up, withdraw or drop out. A participant will be considered lost to follow-up if he/she is unreachable for at least two consecutive visits by the study site until the end of the study. And so, for these participants, observations will be censored from the date of last observation.

In addition, for participants still being followed in the study but whose observation is missing at week 48 and at the 30-day visit after week 48, data will be censored at the last observation.

Partial dates will be extrapolated. For example, all dates saved as NK/FEB/2020 will be recoded as 15/FEB/2020 and those saved NK/NK/2020 will be recoded as 30/JUNE/2020. NK means not known.

For the assessment of HIV RNA viral load reduction at week 12, we will use the last observation carried forward approach to fill in missing data at visit 12.

For all continuous variables used as endpoint, if the value is missing at week 48 and the value at the 30-day visit after week 48 is not missing, it will be used to replace the missing week 48 value whether or not the patient has been switched off the study drug.

For participants who stop the study prematurely, if the Early Termination Visit (ETV) is performed, the value will be used to complete the nearest missing visit.

For participants for whom the date of onset of the clinical event used as an endpoint is missing, the missing date of onset will be replaced by the event reporting date.

For patients reported outcomes, we will used multiple imputation approach to fill in missing data.

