3.2 RANDOMISATION SCHEME AND BLINDING

The randomization list will be generated by an independent statistician not part of the study team. The list will be generated by a centralized computer-generated random list with a permuted block size. He is the only person who know the size of the blocks.

Participants will be randomly assigned, in a 1:1 ratio, to receive a BIC containing regimen or boosted PI containing regimen for 48 weeks, with allocation stratified by country and baseline CD4 cell count (<50 cells/µL, 50-199 cells/µL, or ≥200 cells/µL).

Randomization will be done at the baseline visit (date of the study treatment initiation). This study is open-label; therefore, all investigators, site pharmacists, study nurses and participants will be unmasked and aware of the treatment allocation throughout the study.

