7.1 PRIMARY EFFICACY ANALYSIS

Endpoint

The primary endpoint is the first occurrence of any of the following components:

1. Virological failure
 - a) Insufficient virological response, either:
 - a. HIV-1 RNA reduction < 1 log 10 copies/mL at week 12, or
 - b. Viral load > 50 HIV-1 RNA copies/mL at week 48
 - b) Viral rebound, which is subsequently confirmed at the following scheduled or unscheduled visit, defined as either:
 - a. Rebound of HIV-1 RNA to >200 copies/mL after having achieved HIV-1 RNA <50 copies/mL
 - b. Rebound of HIV RNA by >1 log 10 copies/mL from nadir value, for patients whose viral load has never been suppressed below 50 copies/mL
2. Clinical events¹
 - a) Death related to HIV, AIDS, OI/severe BI or complications of therapy including IRIS
 - b) Any new or recurrent AIDS defining event on, or after 28 days of therapy
 - c) Any new serious non-AIDS defining event documented by the endpoint review committee (including severe BI, end stage liver disease, renal failure, cardiovascular event, and non-AIDS related malignant disease)
 - d) Clinically relevant AEs of any grade or IRIS which require treatment interruption (lasting > 5 days) of INI or boosted PI therapy within the first 48 weeks after randomisation. Discontinuation of BIC or boosted DRV followed by (within 5 days) continuation with another INI or PI, respectively, is not considered as a strategy failure or endpoint.

Descriptive statistics and graphical representation

The analyses will be performed with the mITT population and DPS1. Data will be summarized with the number and percentage of participants with an event. Kaplan-Meier curves will also be plotted for the primary endpoint and its component.

A table, listing for each participant any event, they may have had as well as the day from baseline to event onset, will be generated.

Statistical methodology

The proportion of patients with an event will be estimated using the Kaplan-Meier method. Episodes of clinical events diagnosed at baseline will not be considered as incident events in the study. For virological events evaluation data were censored at the time of treatment discontinuation.

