The follow-up will begin at baseline and continue until the week 48 visit, study discontinuation, loss to follow-up, or onset of the composite primary endpoint events; whichever occurs first. Participants lost to follow-up or who have discontinued the study when they are endpoint free at time of leaving the study will be censored at the date of last observation.

The effect of study treatment will be assessed using Cox regression model with treatment group and adjustments for stratification factor (country/group of neighbouring countries and baseline CD4 cell

counts ($<50/\mu\text{L}$ or $\geq50/\mu\text{L}$), as the sample size would not allow use of the stratification factors of randomisation (country and baseline CD4 in three categories (<50 ; $50-199$; $\geq200/\mu\text{L}$)). An adjusted hazard ratio (HR) and the associated 95% Confidence Interval (CI) will be calculated. Separate analyses for each component of the primary endpoint will be done. All P-values will be two-tailed with a significant level at 5%.

A sensitive analysis will be performed with the per-protocol population and DPS2.

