7.2.8 Incidence of hospitalisation

Endpoints

The endpoint is the first occurrence of hospitalisation over the 48-week visit. Hospitalisation occurring before the initiation of study treatment (baseline) will not be considered in the analysis.

Descriptive statistics and graphical representation

The analyses will be performed with the mITT population and DPS1. Data will be summarized with the number and percentage of hospitalised participants. The Kaplan-Meier curves will also be plotted.

Statistical methodology

The incidence of hospitalisation will be estimated with the Kaplan-Meier method. The follow-up will begin at baseline (date of study treatment initiation) and continue until the week 48 visit, study discontinuation or death, loss to follow-up, or hospitalisation; whichever occurs first.

The effect of study treatment will be assessed using Cox regression model with treatment group and adjustments for stratification factor (country/group of neighbouring countries and baseline CD4 cell counts (<50 or $\geq 50/\mu\text{L}$)). An adjusted hazard ratio (HR) and the associated 95% Confidence Interval (CI) will be calculated.

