8. SAFETY ANALYSES

Endpoints

Safety endpoints include the following endpoints:

- Cumulative incidence of any adverse events (AEs: grade \geq 2), separately grade 2, 3 and 4 AE
- Cumulative incidence grade 3 or AEs
- Cumulative incidence of drug-related AEs (all grade)
- Cumulative incidence of drug-related grade 3 and 4 AEs
- Cumulative incidence of serious adverse events (SAE)
- Cumulative incidence of AE leading to study/treatment
- Cumulative incidence of laboratory toxicities
- Death

Participants with multiple adverse events on a given day will be considered as having one adverse event on that day. Adverse events occurring before the initiation of study treatment (baseline) will not be considered in the analysis.

Descriptive statistics and graphical representation

All analyses on safety endpoints will be performed on the Safety analysis set. All observed data will be included in the analysis set.

Any AE (grade \geq 2), grade 3 or 4 AE, SAE, drug-related SAE, grade 2, 3 and 4 AEs, drug-related grade 3/4 AE, drug-related AEs (all grade), discontinuation of study/treatment due AEs, laboratory toxicities and death will be summarized with the total number of events, number and percentage of participants with at least one event and the incidence rates per 100 person-years of these events by treatment group (BIC versus DRV/c). The most frequent drug-related grade 3 or 4 AEs will be reported.

Statistical methodology

The incidence rates of each endpoint of interest will be calculated by the total number of events from baseline to week 48 visit divided by the total number of person-years. In this analysis, the entire

follow-up will be considered (i.e. follow-up will begin at baseline and continue until the week 48 visit, study discontinuation or death, loss to follow-up; whichever occurs first). The duration in years of participation for each subject will be calculated by the difference between the date of the last observation and the date of date of study treatment initiation plus one, divided by 365.25. The person-years is the total sum of the number of years that each member of a study population has been under observation.

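### The SAP's partial-date rule has no bound at first dose or end of observation, so on-treatment events can be dated before baseline; adverse events and hospitalisations so dated would be dropped.

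*Combined protocol and SAP*

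**What the plan says.** SAP 5.3 gives the rule for partial dates by example: "all dates saved as NK/FEB/2020 will be recoded as 15/FEB/2020 and those saved NK/NK/2020 will be recoded as 30/JUNE/2020". It names no lower limit at first dose and no upper limit at report, last contact or death. Section 9.7 of the protocol, on missing data, has no partial-date rule.

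The same SAP section has a separate sentence for clinical events used as endpoints, under which "the missing date of onset will be replaced by the event reporting date". It is worded for a missing date, and the SAP does not say whether a partial date counts as missing.

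Other sections make event status depend on the date:

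- SAP 3.2 makes the baseline visit the day of randomisation and of treatment start.
- SAP 7.1, primary endpoint: "The follow-up will begin at baseline and continue until the week 48 visit", and "Episodes of clinical events diagnosed at baseline will not be considered as incident events in the study". The AIDS component is "Any new or recurrent AIDS defining event on, or after 28 days of therapy".
- SAP 7.2.7 leaves out IRIS diagnosed at baseline.
- SAP 7.2.8: "Hospitalisation occurring before the initiation of study treatment (baseline) will not be considered in the analysis".
- SAP 8: "Adverse events occurring before the initiation of study treatment (baseline) will not be considered in the analysis".

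**The concern.** The imputed date takes no account of when the participant was first dosed. Anyone who starts treatment on the 16th or later, and has an event later that month with the day unknown, gets an event date before treatment began. If only the year is known, the same happens to anyone who starts after 30 June and has the event before the year ends.

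For adverse events and hospitalisations, the text then removes a true on-treatment event. For the primary endpoint and IRIS, it produces a negative event time that the SAP does not say how to handle. With no upper bound, an event can also be dated after follow-up has ended. The rule can also move an AIDS event across the 28-day limit in either direction, which changes whether it counts.

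This is a stated rule that gives a wrong answer in identifiable cases, and it can be repaired before the SAP is signed.

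**Working it through.** **Worked cases from the rule (day 0 = first dose)**

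| First dose | True event | Recorded as | Imputed | Result |
|---|---|---|---|---|
| 20 Feb 2020 | 27 Feb 2020, day 7 | day unknown | 15 Feb, day -5 | before baseline |
| 1 Sep 2020 | 20 Nov 2020, day 80 | year only | 30 Jun, day -63 | before baseline |
| 20 Jan 2020 | 25 Feb 2020, day 36 | day unknown | 15 Feb, day 26 | AIDS event stops counting |
| 12 Jan 2020 | 3 Feb 2020, day 22 | day unknown | 15 Feb, day 34 | AIDS event starts counting |

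The largest possible shift is 16 days with the day unknown and 184 days with only the year known.

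**How often, given that a date is partial**

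Assumptions (mine, not in the documents): every first-dose date in a four-year period is equally likely, and true event days are uniform within the window. Each combination was enumerated and the imputed date compared with first dose and with day 343 (week 48 = day 336, plus the 7-day visit window).

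| True event window | Day unknown: before first dose | Year only: before first dose |
|---|---|---|
| Days 1-14 | 26.1% | 48.3% |
| Days 1-28 | 13.1% | 46.4% |
| Days 1-336 | 1.1% | 13.7% |

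Over days 1-336, 0.3% (day unknown) and 12.3% (year only) are dated after day 343.

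Put another way, if partially dated events are spread evenly over 48 weeks, it takes about 1/0.0109 = 92 of them with the day unknown to put one before baseline. With only the year known it takes about 1/0.137 = 7.

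**The 28-day rule (AIDS component only)**

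Of true day 28-55 events, 14.9% (day unknown) or 46.7% (year only) are moved below day 28. Of true day 0-27 events, 12.3% or 45.7% are moved to day 28 or later. A lower bound at or just after first dose removes all dates before baseline but leaves these four shares unchanged.

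**Scale against the design**

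The plan's event target reproduces:

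events = 4 × (1.960 + 0.842)² / (ln 1.606 - ln 0.909)² = 31.40 / 0.5692² = 96.9, rounded up to 97.

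With average failure (25% + 23%)/2 = 24%, 97/0.24 = 404 subjects, as stated.

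Power with D events is Φ(√(D/4) × 0.5692 - 1.960). This shows what losing primary events would cost, if any were lost:

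| Events lost from 97 | Non-inferiority power |
|---|---|
| 0 | 80.0% |
| 1 | 79.6% |
| 2 | 79.2% |
| 5 | 77.9% |
| 10 | 75.6% |

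**The case against.** The strongest reply is that few on-study dates will be partial. Protocol 8.2 has onset time after dosing documented, 8.2.4 collects start and end dates for serious events, and section 11 has the monitor query missing data. Virological failures are dated from samples. Year-only dates are the least likely case for on-study events. This stands, and it is why the 48-week figure of about 1% with the day unknown matters more than the year-only figures.

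Safeguards also exist. The endpoint committee validates clinical events, SAP 7.1 lists the day from baseline to event onset (so negative days would show), and SAP 5.1 provides a mock-up report before sign-off. SAP 5.3 offers its dates as examples, so adding a bound contradicts nothing. These make detection likely, but none says what to do with a date before first dose, and the committee's stated role does not cover all adverse events or hospitalisations.

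The reporting-date sentence might be read to cover partial onset dates of endpoint events. Events reported on study would then not precede baseline. The SAP does not say so, and the sentence does not reach adverse events in general. A late report could still carry an early AIDS event past day 28.

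Three stronger readings are tempting, and the documents do not support them.

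- A reader might infer that the SAP expressly drops misdated primary events. It excludes events diagnosed at baseline, which describes clinical status rather than an imputed date. Loss is an inference from the negative time.
- A reader might infer that the damage is concentrated because IRIS and adverse events cluster in the first weeks. SAP Appendix 4 describes unmasking in the first weeks of therapy, but gives 3-12 weeks as usual for MAC and for the early CMV forms, and two weeks to 11 months for cryptococcal IRIS. The first-four-weeks statement concerns TB, and active TB is an exclusion. No timing is given for adverse events.
- A reader might infer bias towards one arm. The rule is identical in both arms and the documents show no direction.

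**Conclusion.** The gap is real and minor. SAP 5.3 as written can date on-treatment events before first dose, and for adverse events and hospitalisations the SAP then removes them. For the primary endpoint and IRIS it leaves an undefined negative time rather than a stated exclusion. The missing upper bound matters mainly for year-only dates.

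Every percentage applies only to partially dated events, under uniform start dates and event days; earlier true timing would raise them. The documents do not say how many partial dates there are, so no absolute loss can be computed. Because such dates should be uncommon, the overall effect is probably small. The 28-day problem is separate, affects only the AIDS component, and is not solved by a bound.

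**What to change.** Add to SAP 5.3:

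> For events known to have started after first dose, the imputed date will be no earlier than the day after first dose and no later than the earliest of the report date, last contact and death; such events are counted as incident.

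The day after first dose is deliberate: a date equal to first dose would put the event at baseline, where it could still be excluded.

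Then:

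- State whether the reporting-date rule for missing onset of endpoint events also applies to partial dates.
- Where the possible dates of an AIDS event span day 28, have the existing endpoint committee assign the date without knowledge of arm. Protocol v5.0, 8.3.6, has that committee reviewing unblinded data, so masking for this task must be written down.
- Add a sensitivity analysis using the earliest and latest possible dates.

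The cost is a few sentences, slight extra programming and a small committee task. Some date error remains, and the bound works only where onset after dosing is recorded, as protocol 8.2 requires. The SAP is at v0.3 and section 5.1 allows updating before sign-off, so this can be settled before the final analysis.

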5 ELIGIBILITY CRITERIA

5.1 Inclusion criteria

Patients must meet all the following inclusion criteria to be eligible for participation into this study.

1. The ability to understand and sign a written informed consent form (ICF) and must be willing to comply with all study requirements.
2. Male or non-pregnant, non-lactating females[†].
3. Age \geq 18 years.
4. Have documented, untreated HIV-1 infection with either:
 - a) AIDS with any CD4 cell count (AIDS-defining conditions are listed within Appendix 3).

Or

- b) Severe bacterial infection (BI)[‡] and must have a CD4 cell count $< 200/\mu\text{L}$ within 28 days prior to study entry[§].

Or

- c) Any symptoms or no symptoms and must have a CD4 cell count $< 100/\mu\text{L}$ within 28 days prior to study entry and must have an entry HIV viral load > 1000 copies/mL.

Or

- d) Currently receiving treatment for OI^{**}.
 - i. Subjects with other serious OIs, including other AIDS-defining and AIDS-related OIs for which appropriate therapy other than ART exists are eligible, but Investigator approval must be obtained.
 - ii. Current OI treatment can have been discontinued prior to start of ART.

5. Have an entry HIV viral load > 1000 copies/mL
6. Have the ability to take oral medications.

[†] Male and female sex are defined as sex at birth. For transgender participants ≥ 13 years of age who have been on hormone therapy for more than 6 consecutive months, grade haemoglobin based on the gender with which they identify (i.e. a transgender female should be graded using the female sex at birth haemoglobin laboratory values)

[‡] A severe BI consists of any of bacterial pneumonia, IBI or any bacterial infectious disorder with grade 3 severity (severe or medically significant but not immediately life-threatening, see Appendix 2) or requiring unscheduled hospital admission. An IBI is defined as the isolation of a bacterial organism from a normally sterile body site, or for bacterial nucleic acid to be detected at a normally sterile body site. Sterile body sites include blood, cerebrospinal fluid, pleural fluid, pericardial fluid, peritoneal fluid, joint fluid, bone aspirate, or a deep tissue abscess.

[§] Study entry is defined as the start of the screening process

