5.2.1 Full Analysis Population

Modified Intention-to-treat (mITT) analysis set: all randomised participants who received at least one dose of study drug. Participants will be included in the analyses according to the planned randomised intervention.

The following data points sets are defined:

- **DPS1:** All observed data will be included in the analysis set regardless of study intervention discontinuation and/or receipt of rescue therapy
- **DPS2:** For participants who discontinue study intervention and/or receive rescue therapy, post-discontinuation or post-rescue observations will be excluded.

The mITT and DPS1 will be used to estimate the primary endpoints and the all secondary endpoints.

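### The week-12 carry-forward rule does not exclude the baseline viral load, so a participant with no result between baseline and week 12 is scored as a virological failure that nobody observed

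*Combined protocol and SAP*

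**What the plan says.** SAP section 5.3 (Handling of missing data) deals with a missing week-12 viral load in one sentence: "we will use the last observation carried forward approach to fill in missing data at visit 12". It does not require the carried value to be post-baseline, or the participant to be in follow-up at week 12.

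SAP section 7.1 counts "HIV-1 RNA reduction < 1 log 10 copies/mL at week 12" as a primary event. Confirmation at a later visit is required for viral rebound but not for this criterion. The primary analysis set in SAP 5.2.1 is "all randomised participants who received at least one dose of study drug", so no post-baseline viral load is needed to be analysed.

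Other rules bear on the same participants:

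- SAP 5.3, on loss to follow-up (unreachable for at least two consecutive visits, through to the end of the study): "for these participants, observations will be censored from the date of last observation".
- SAP 7.1, on people who leave without an event: "Participants lost to follow-up or who have discontinued the study when they are endpoint free at time of leaving the study will be censored" at their last observation.
- SAP 7.1 ends follow-up at the earliest of the week-48 visit, study discontinuation, loss to follow-up or the first event. It also censors virological evaluation when treatment is stopped.
- SAP 5.3 uses an early termination visit value, where there is one, to fill the nearest missing visit.

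Protocol v5.0 sections 9.3.3 and 9.7 name carry-forward only for CD4 and CD8 measures. Its use on a component of the primary endpoint comes from the SAP.

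**The concern.** Carrying forward an on-treatment value makes some use of the participant's response. Carrying forward the pre-treatment value assumes no response at all, and the week-12 criterion turns that assumption into a primary event.

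This differs from how the SAP treats missing data elsewhere. A participant with no result at week 48 or at the 30-day visit after it is censored, not failed. The snapshot analysis in SAP 7.2.2 keeps loss to follow-up apart from viral load at or above 50 copies/mL.

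At stake are primary events that reflect missed visits and not drug failure. If they are equal in the two arms, they dilute a true difference. If they are unequal, which is possible in an open-label trial, they bias the hazard ratio towards whichever arm lost fewer early results.

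**Working it through.** **1. The plan's own figure.** SAP section 4 gives a margin of 1.606, an expected hazard ratio of 0.909, 80% power and a two-sided 95% interval. Events = 4 × (1.960 + 0.842)² / (ln 1.606 − ln 0.909)² = 96.9, so 97. Evaluable N = 97 / [(0.25 + 0.23)/2] = 404. Both match the plan.

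**2. What the rule does.** Protocol v5.0 section 5.1 requires participants to "have an entry HIV viral load > 1000 copies/mL". Call the baseline value V. With V carried to week 12, the reduction is log10(V) − log10(V) = 0, which is below 1 for any V. Every participant with only a baseline value fails.

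**3. Who reaches the rule.**

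| Participant, no viral load after baseline up to week 12 | SAP 5.3 carry-forward | SAP 7.1 |
|---|---|---|
| Still in follow-up and on treatment, returns after week 12 | Failure at week 12 | No censoring rule applies; the first event stands even if later suppressed |
| Leaves or is lost before week 12 | Failure at week 12, read literally | Follow-up ends earlier, which points to censoring |
| Stops treatment before week 12, stays in the study | Failure at week 12, read literally | Virological evaluation censored when treatment stops |

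For the first row nothing in the SAP corrects the result. For the other two, section 7.1 points to censoring, but section 5.3 does not say so.

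**4. How many.** The documents give no share of participants with only a baseline value. The nearest figure is about 7.5% dropout per year (SAP section 4). If it is spread evenly, 1 − 0.925^(4/52) = 0.6% leave before week 4, or 2.6 of 440, and 1 − 0.925^(12/52) = 1.8% leave before week 12, or 7.8 of 440. These are leavers, most of whom section 7.1 would censor, so they only indicate scale. Returners cannot be estimated from the documents.

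**5. Illustration: an equal share f per arm scored as failures.** Each arm's failure probability becomes p′ = f + (1 − f)p. Then HR = ln(1 − p′ INI) / ln(1 − p′ PI), and events d = 220 × (p′ INI + p′ PI). The chance of declaring non-inferiority is Φ[(ln 1.606 − ln HR) × √d / 2 − 1.96]. The error is computed with 37% against 25%, power with 23% against 25%.

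| f per arm (participants) | HR at the margin | One-sided error | HR at design | Power |
|---|---|---|---|---|
| 0 | 1.606 | 2.5% | 0.909 | 83.3% |
| 0.5% (1.1) | 1.596 | 2.7% | 0.910 | 83.7% |
| 1% (2.2) | 1.586 | 3.0% | 0.912 | 84.0% |

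Power starts above 80% because all 440 participants give 220 × 0.48 = 105.6 expected events, not 97. A Cox simulation at f = 1% (1,000 runs) gave an error of 3.7% with carry-forward and 2.9% with censoring. That agrees in direction, within simulation error.

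**6. Illustration: imbalance.** Put k artificial failures in one arm of 220, with p′ = [p(220 − k) + k]/220. From a hazard ratio of 0.909, one in the INI arm only gives 0.924, and one in the PI arm only gives 0.894. Three give 0.956 and 0.867.

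**The case against.** The best reply is that SAP 7.1 already sets an order. Follow-up stops at the earliest of discontinuation, loss or event, so a person who leaves before week 12 is out of the risk set before a week-12 failure could be dated. Stopping treatment has the same effect on virological evaluation. This stands, and it covers most leavers. A reader might infer that the SAP gives opposite primary outcomes to every early leaver. The documents do not support that: for leavers, what is missing is a sentence in section 5.3 deferring to section 7.1.

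A reader might also think of early deaths. Deaths related to HIV, AIDS, infection or therapy are already primary events, and for other deaths observation has ended before week 12.

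The group is narrow as well. Viral load is scheduled at weeks 4, 8 and 12, and an early termination value fills a gap. SAP 7.1 asks for a listing of every event by participant and for separate component analyses, and SAP 5.1 provides for a mock-up run and update before sign-off. Artificial failures would therefore be visible. Being visible does not settle how to score them, and none of these points covers the participant who misses the early visits and returns.

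**Conclusion.** The point holds for the rule as written. Because baseline is not excluded, SAP 5.3 produces an unobserved primary event for any participant in follow-up and on treatment with no viral load after baseline up to week 12. For leavers the rule is only under-specified.

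The effect is probably small. At an assumed equal 0.5% to 1% per arm, the one-sided error at the margin is about 2.7% to 3.0% against 2.5%.

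Two stronger readings should be resisted. The first is a large inflation of error or loss of power. That needs several percent of an arm to have only a baseline value, or a marked imbalance, and the documents give no basis for either. The second is that the rule always helps non-inferiority. Equal artificial events pull the hazard ratio towards 1, which moves it away from the margin only when the true ratio is above 1. At the design value of 0.909 the ratio moves slightly towards the margin, and the added events roughly offset this in the power figure. Imbalance can bias the result in either direction.

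The sizes rest on assumed shares, evenly timed dropout and a normal approximation. The defect in the wording does not depend on them.

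**What to change.** Replace the week-12 sentence in SAP section 5.3 with wording such as:

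> LOCF at week 12 uses only post-baseline viral loads measured on or before week 12, in participants still in follow-up and not yet censored for virological evaluation at week 12; the baseline value is never carried forward. Censoring under section 7.1 takes priority over LOCF. A participant in follow-up with no post-baseline viral load by week 12 is not classified on the week-12 criterion and remains at risk for all later virological and clinical components.

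The limit on or before week 12 matters: without it, a returning participant has a post-baseline value later on, and baseline could still be carried to week 12. The last sentence keeps a participant with a clinical endpoint from being censored merely for lack of a viral load.

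The cost is a few lines in a SAP (v0.3) that has yet to be signed off. There is a small downside: leaving these participants unclassified assumes that the missing values say nothing about response. Report a sensitivity analysis that counts them as week-12 failures, and give their number by arm.
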